1.3 Study Design

This is an 8+8 weeks, randomized, double-blind, multi-center, placebo controlled, parallel group study to include adult patients with moderate to severe active Ulcerative Colitis. The study consists of an 8-week blinded treatment phase, followed by 8-week of blinded active arms extension phase. The primary endpoint is assessed at the end of treatment phase at week 8.

Eligible subjects will be randomized to either one of the 3 doses of active drugs or placebo in 1:1:1:1 ratio for 4mg QD, 4mg BD, 8mg QD and placebo group respectively for treatment phase. The total number of subjects to be randomized is 152. There will be a total of 9 outpatient clinic visits. Subjects randomized into placebo in treatment phase will also have a pre-assigned randomized treatment sequence for extension phase, which are 3 active groups (placebo -> 4mg QD, placebo -> 4mg BD, and placebo -> 8mg QD) in a 1:1:1 ratio. Subjects randomized to the active arms for treatment phase will remain in the same dose group in the extension phase.

At Visit 1 (screening), subject will be screened and if the subject meets the inclusion/exclusion criteria, the subject can be consented and enrolled into the study with a subject identifier number.

At Visit 2 (Day 0), subject will be randomized into the study if there is no further change to subject's criteria.

After randomization, the subject will be followed-up at week 1, week 4, and week 8, corresponding to Visit 3, Visit 4, and Visit 5 at treatment phase respectively. At Visit 5 (week 8) the primary endpoint assessment will be conducted. Following this treatment phase, subjects have the option to enroll into a further 8 weeks of active arms extension phase.

All subjects that have completed the initial 8 weeks (non-responders or responders) have the option to enter a blinded active arm 8-week extension phase according to the group they were randomized to for extension phase. All subjects have the option not enrolling into the extension phase after first 8 weeks of treatment. All subjects in the extension phase are followed-up for further 2 weeks until week 18 (last visit). Subjects who have completed the first 8-week of treatment phase, but decided not entering into extension phase are required to attend the 2-week follow-up visit. Early withdrawn subjects during the first treatment phase cannot enter the extension phase.

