6.1.2 Study Drug Administration

Study medication will be self-administered by the subject twice daily, one (2 tablets) in the morning, another (2 tablets) in the afternoon. Approximately 8 - 12 hours between the morning and afternoon doses.

However, at baseline (Day 0) the first dose will be taken in the clinic. At Week 4 and at the end of treatment (Week 8) subjects should take their morning oral dose at the clinic. Study medication may be taken with or without food.

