7.3.12 Definition of AE

Any untoward medical occurrence in a patient or clinical investigation subject, temporally associated with the use of a medicinal product, whether or not considered related to the medicinal product.

Note: An AE can therefore be any unfavorable and unintended sign (including an abnormal laboratory finding), symptom, or disease (new or exacerbated) temporally associated with the use of a medicinal product. For marketed medicinal products, this also includes failure to produce expected benefits (i.e., lack of efficacy), abuse or misuse.

Events meeting the definition of an AE include:

- Exacerbation of a chronic or intermittent pre-existing condition including either an increase in frequency and/or intensity of the condition
- New conditions detected or diagnosed after study treatment administration even though it may have been present prior to the start of the study
- Signs, symptoms, or the clinical sequelae of a suspected interaction
- Signs, symptoms, or the clinical sequelae of a suspected overdose of either study treatment or a concomitant medication (overdose per se will not be reported as an AE/SAE).

“Lack of efficacy” or “failure of expected pharmacological action” per se will not be reported as an AE or SAE. However, the signs and symptoms and/or clinical sequelae resulting from lack of efficacy will be reported if they fulfil the definition of an AE or SAE.

Events that **do not** meet the definition of an AE include:

- Medical or surgical procedure (e.g., endoscopy, appendectomy); the condition that leads to the procedure is an AE
- Situations where an untoward medical occurrence did not occur (social and/or convenience admission to a hospital)
- Anticipated day-to-day fluctuations of pre-existing disease(s) or condition(s) present or detected at the start of the study that do not worsen
- The disease/disorder being studied, or expected progression, signs, or symptoms of the disease/disorder being studied, unless more severe than expected for the subject's condition

AEs which meet all of the following criteria:

- Serious
- Unexpected (as per assessment according to safety information in Investigator Brochure)
- There is at least a reasonable possibility that there is a causal relationship between the event and the medicinal product

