### **16.1.1 All TEAEs**

An overall summary of TEAEs in treatment phase will be provided. The number and percentage of patients experiencing AEs and the number of TEAEs will be tabulated.

Incidence of TEAEs will be presented by System Organ Class (SOC) and Preferred Term (PT) and summarized in treatment phase for each SHR0302 dose level , placebo and overall.

All TEAEs during the whole study period will also be summarized for the following groups similarly.

- 8 mg QD total: 8mg QD during the whole study period+ Placebo->8mg QD group after treatment phase
- 4 mg BD total: 4 mg BD during the whole study period + Placebo->4mg BD group after treatment phase
- 4 mg QD total: 4 mg QD during the whole study period + Placebo->4mg QD group after treatment phase
- Placebo only: Placebo group during treatment phase

Incidence of TEAEs will also be broken down further as shown in the following sections.

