## Algorithm for TEAEs by Study Phase for Onset

TEAE START DATE	ACTION
Known	If start date < week 8 visit date, then TEAE in treatment phase If week 16 visit date $\geq$ start date $\geq$ week 8 visit date, then TEAE in extension phase If start date $>$ week 16 visit date, then TEAE in follow up phase
Partial, but known components can determine the phase	If start date < week 8 visit date, then TEAE in treatment phase If week 16 visit date $\geq$ start date $\geq$ week 8 visit date, then TEAE in extension phase If start date $>$ week 16 visit date, then TEAE in follow up phase
Partial and known components can not determine the phase	Missing day - Impute the 1st of the month unless month is same as month of first dose of study drug then impute first dose date Missing day and month – impute 1st January unless year is the same as first dose date then impute first dose date  If the imputed start date < week 8 visit date, then TEAE in treatment phase If week 16 visit date $\geq$ imputed start date $\geq$ week 8 visit date, then TEAE in extension phase If imputed start date $>$ week 16 visit date, then TEAE in follow up phase
Other missing status	impute first dose date and treat the onset of TEAE as in treatment phase

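### SAP Appendix 2 puts adverse events starting on the Week 8 visit date in the extension phase: a placebo subject's event then counts under SHR0302, or in none of the four defined columns if the extension is declined

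*SAP*

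**What the plan says.** The phase table in SAP Appendix 2 reads "If start date < week 8 visit date, then TEAE in treatment phase". Onsets from the Week 8 date up to and including the Week 16 date meet the next condition, which ends "week 8 visit date, then TEAE in extension phase". Anything after the Week 16 date is follow-up. These conditions stand in the row for known dates, so they are not confined to partial dates.

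The protocol places Visit 5 inside the treatment phase. Section 1.3 lists the Week 1, 4 and 8 visits as "corresponding to Visit 3, Visit 4, and Visit 5 at treatment phase respectively". The Time and Event Table heads Visit 5 as the end of that phase. Section 5.8 counts anyone who leaves before finishing Visit 5 procedures as an early withdrawal.

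SAP 16.1.1 gives the main event tables for the treatment phase, then a whole-study version with four groups. An active column is, for example, "8mg QD during the whole study period+ Placebo->8mg QD group after treatment phase". The placebo column is "Placebo only: Placebo group during treatment phase".

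The extension is optional. Completers who "decided not entering into extension phase are required to attend the 2-week follow-up visit", and Protocol 6.1 dispenses no drug to them at Week 8.

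**The concern.** Haematology, chemistry, lipids, thyroid tests and ECG are all scheduled at Visit 5. Protocol 7.3.12 says "An AE can therefore be any unfavorable and unintended sign (including an abnormal laboratory finding" and so on, so a result from that visit can be an adverse event. If its onset is recorded as the sample date, the phase rule takes it out of the treatment phase.

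Two things are at stake. First, the treatment-phase tables are the ones that set each dose beside placebo over the same eight randomized weeks, and they would miss events dated to the closing visit. Second, attribution goes wrong for placebo subjects: an abnormality found after eight weeks of placebo would be counted under a drug not yet taken, or in no treatment column. The by-visit laboratory tables use nominal visits, so they would show the same finding at Week 8 under placebo, and the two outputs would disagree.

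**Working it through.** The plan states no figure here, so the check applies the written rules to test onsets.

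**Inputs.** Week 8 = Day 56 and Week 16 = Day 112 (Time and Event Table, nominal days). Phase conditions are from SAP Appendix 2 and columns from SAP 16.1.1. Decliners have no Week 16 visit. Early withdrawals have neither a Week 8 nor a Week 16 visit.

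**Conditions.** Treatment: onset < 56. Extension: 56 ≤ onset ≤ 112. Follow-up: onset > 112.

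| Subject | Onset | Phase | Whole-study column |
|---|---|---|---|
| Placebo, enters extension | Day 55 | treatment | Placebo only |
| Placebo, enters extension | Day 56 | extension | an SHR0302 total |
| Placebo, enters extension | Day 57, 70 | extension | an SHR0302 total |
| Placebo, declines | Day 55 | treatment | Placebo only |
| Placebo, declines | Day 56, 57, 70 | none assignable | none of the four |
| Active, enters extension | Day 55 | treatment | own dose total |
| Active, enters extension | Day 56 | extension | own dose total |
| Active, declines | Day 56, 57, 70 | none assignable | own dose total |

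For a decliner, Day 56 fails the treatment condition because 56 < 56 is false. The other two conditions need a Week 16 date that does not exist. The gap therefore covers the whole follow-up period, not one day. For an early withdrawal the treatment condition itself cannot be evaluated, and the SAP does not say what then applies. A subject who leaves during the extension has no Week 16 date to close that phase.

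**Reach.** 152 / 4 = 38 placebo subjects; 38 × (1 − 0.08) = 35 are expected to reach Visit 5. This counts subjects to whom the rule applies, not misallocated events.

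**With the change proposed below.** Day 56 in a decliner becomes treatment phase, under Placebo only or the dose received. Days 57 and 70 become follow-up, with a placebo row. Day 56 in an active-arm entrant becomes treatment phase. Day 56 in a switching placebo subject becomes treatment phase when onset is known to precede the first extension dose.

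**The case against.** The best defence is that Week 8 is a switch day. Extension drug is dispensed then (Protocol 6.1), SAP 13.1 assumes dosing from the morning of the dispensing visit, and SAP 6.2 counts events starting on a first-dose date as post-baseline. Giving same-day events to the new treatment is conventional and cautious, because it adds events to SHR0302. Closing the extension inclusively at Week 16 is then consistent, since no new treatment starts there.

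That stands for untimed events in placebo subjects who switch. It does not cover decliners, who get no further drug; active arms, which keep the same dose; or findings made before any extension dose. Protocol 6.1.2 says "at the end of treatment (Week 8) subjects should take their morning oral dose at the clinic", but the documents do not give the kit used or its order relative to sampling.

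A reader might infer more than the text supports:

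- *The Week 8 laboratory and ECG signal is lost.* It is not. By-visit values, abnormality counts and shift tables follow nominal visits (SAP 6.4, 16.3, 16.4).
- *Decliners' events vanish.* SAP 16.1.1.1 to 16.2 include an overall column that may hold them, and every event is listed.
- *A stop prompted by Week 8 blood is wrongly missing from the treatment-phase discontinuation table.* A subject who has finished Visit 5 is not an early withdrawal under Protocol 5.8, and the central laboratory result would normally stop extension dosing, so its absence is arguably right.

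**Conclusion.** The concern holds as a misallocation of reported adverse events at one boundary, plus missing branches for subjects without a Week 8 or Week 16 visit. It is worth correcting because a written rule conflicts with the protocol's own phase definition, and with the SAP's principle that safety is analysed by treatment received (SAP 5.5).

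For laboratory and ECG findings it rests on one assumption: that onset is recorded as the sample or tracing date. Active-arm events stay in their own whole-study column, the phase rule is the same in every arm, and SAP 16 plans no statistical comparison of safety data unless specified.

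A reader might infer that a definite share of the drug–placebo difference disappears. The documents give no per-visit event rates, so no such share can be derived. If onsets were spread evenly over Days 0 to 56, the boundary would move 1/57 = 1.8% of events. Findings from a scheduled visit cluster on that date, so their share would be larger by an unknown amount.

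**What to change.** Amend the phase table in SAP Appendix 2:

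- **No extension dose taken:** the treatment phase includes the Week 8 visit date, or the early withdrawal visit if there is no Week 8 visit. Later events are follow-up, shown under the treatment actually received. Add a placebo follow-up row to SAP 16.1.1.
- **Extension entered:** an onset on the Week 8 date known to precede the first extension dose is treatment phase. Active-arm subjects, whose dose does not change, use onset on or before the Week 8 visit date. Untimed events on that date in switching placebo subjects may stay in the extension phase.
- **Extension entered, no Week 16 visit:** the extension phase ends at the last extension dose, and later events are follow-up.

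The cost is a few lines in Appendix 2 and one row in 16.1.1. Dosing times are already taken from the diary (SAP 13), and SAP 16.1 already refers to onset time. No document shows an eCRF field linking an event to a sample, so the rule should use recorded onset time and not depend on such a link. The downside is that untimed same-day events in switching placebo subjects still rest on a convention, which the SAP should state.

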## 12. MEDICATIONS AND PROCEDURES

Prior medications are those medications that were stopped prior to first study treatment. Concomitant medications are medications taken at least once after first study treatment. Medications stopped on the same day as first study treatment will be considered as prior medication only.

Prior and concomitant medications will be coded using the World Health Organization Drug Dictionary (WHO Drug Global 01Sep2018\_B3). The PT and Anatomical Therapeutic Chemical (ATC) Classification System level 2 will be used for tabulation. The summary tables will show the number and percentage of patients by PT and ATC level 2, for each treatment group and overall. Only concomitant medications will be summarized. The descriptive summaries for concomitant medications will be presented for the SS. Missing or partial dates for medications will be handled according to Appendix 2 of this analysis plan. In the case where it is not possible to define a medication as prior or concomitant, the medication will be classified by the worst case; i.e. concomitant. For the summaries of concomitant medications, patients who take the same medication (in terms of the PT), more than once will only be counted once for that medication. Prior medications will be listed only.

The detailed information of prior and concomitant medication use including medication name, start date, end date, ongoing or not, primary reason for use, total daily dose, frequency and route of administration, etc. will be listed. Prior and concomitant medications will be listed separately.

The detailed information of procedures will be collected on the “Procedures” form of Electronic Case Report Form (eCRF) including procedure name, start date, end date, ongoing or not, and primary reason for use. Procedure name will be coded using Medical Dictionary for Regulatory Activities Version 21.1 or higher version. Procedures information be will be listed.

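### In the whole-study TEAE tables, the earliest-date rule for unclear onsets credits placebo with events in switched patients that may have begun on SHR0302

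*SAP*

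**What the plan says.** The phase table in SAP Appendix 2 (Algorithm for TEAEs by Study Phase for Onset) handles onset dates in four rows.

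- A fully known date is compared with the Week 8 and Week 16 visit dates. An onset on the Week 8 visit date itself belongs to the extension phase.
- A partial date that already settles the phase ("Partial, but known components can determine the phase") is classified by what is known.
- A partial date that does not settle it is imputed. With the day missing: "Impute the 1st of the month unless month is same as month of first dose", in which case the first dose date is used. With day and month missing: "impute 1st January unless year is the same as first dose date then impute first dose date". The result is then cut at Week 8: "If the imputed start date < week 8 visit date, then TEAE in treatment phase".
- For any other missing status: "impute first dose date and treat the onset of TEAE as in treatment phase".

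The stop date plays no part in this table, although the preceding table, on treatment emergence, does use it. There is no separate provision for patients who change from placebo to drug.

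SAP 16.1.1 defines the whole-study groups. Each dose total is the arm randomised to that dose for the whole study, plus the placebo patients switched to that dose, counted after the treatment phase. The comparator is "Placebo only: Placebo group during treatment phase". Sections 16.1.1.1 to 16.1.5 reuse these groups for relationship, severity, serious infection, discontinuation, serious events and fatal events.

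**The concern.** Taking the earliest date is cautious when the only boundary is the first dose, because it keeps doubtful events treatment-emergent. This trial has a second boundary. Every placebo patient who enters the extension starts SHR0302 at Week 8. At that boundary the earliest date is the less cautious choice, because it places the event in the placebo period.

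The SAP leans the other way in comparable cases. For a drug that cannot be classed as prior or concomitant (SAP 12), "the medication will be classified by the worst case; i.e. concomitant". A serious event with missing relationship is treated as probably related (SAP 16.1.4). An undated event is presumed treatment-emergent (SAP 16.1 and Appendix 2).

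At stake is the comparison of each dose total with placebo in the whole-study TEAE tables. SAP 3.1 says the trial's safety data, among others, will help select one or two doses for further development. Imputed dates are not shown in listings, so a reader would not see the date that decided the column.

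**Working it through.** The plan gives no figure to reproduce, because this is a classification rule. I checked it in three steps.

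**1. One patient traced through the rule.** First dose 20 January 2020; Week 8 visit on Day 56, 16 March 2020; switch to drug. The true onset is 28 March, on drug, but it is recorded only as March 2020. March contains days on both sides of 16 March, so the phase is not settled. The month differs from the month of first dose, so the imputed date is 1 March. That is before 16 March, so the event is treatment phase and is reported under placebo. Had the true onset been 10 April, recorded as April 2020, the known month would settle the phase and the event would stay with drug.

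**2. Enumeration.** Inputs: visits at Day 56 and Day 112 and last visit at Day 126 (protocol 5.12), with the four rows above. Assumptions: onset days uniform over Days 0 to 126, and first-dose dates uniform over 365 consecutive days. True extension-phase onsets number 57 days (Day 56 to Day 112) × 365 = 20,805.

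| Missing part | True extension onsets sent to treatment phase | True treatment-phase onsets sent later |
|---|---|---|
| Day | 5,394 / 20,805 = 25.9% | 0% |
| Day and month | 19,152 / 20,805 = 92.1% | 0% |
| Whole date | 20,805 / 20,805 = 100% | 0% |

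Moving the visits by 3 days either way (53/109 and 59/115) leaves these shares unchanged to three decimals.

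When the unknown day straddles Week 8, every post-switch onset goes to the treatment phase. Two kinds of date escape:

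- A missing-day date that straddles only Week 16 is imputed into the extension phase and stays with drug.
- A year-only date in a year that begins on or after the Week 8 visit is imputed to 1 January and also stays with drug.

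Across all missing-day dates that reach the imputation row, 5,377 + 5,394 = 10,771 go to the treatment phase and 5,381 + 3,853 = 9,234 to the extension. That is 54% and 46% of 20,005.

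**3. Effect of one moved patient.** Placebo: 152/4 = 38. Switchers per dose if all enter the extension: 38/3 = 12.7. Dose total: 38 + 12.7, about 51.

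- Placebo gains 1/38 = 2.6 points.
- The dose total loses 1/51 = 2.0 points.
- The gap moves by 2.6 + 2.0 = 4.6 points.

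This assumes that all randomised patients are dosed, that all 38 placebo patients enter the optional extension, and that the patient has no other event in the same row. Fewer entrants would shrink the dose denominator and raise the figure slightly. With a single switcher on that dose it is 1/38 + 1/39 = 2.6 + 2.6 = 5.2 points.

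**The case against.** The strongest objection concerns the repair. The same algorithm feeds the treatment-phase tables, which are the randomised comparison over equal exposure. There the present rule treats all arms alike. A rule that moved ambiguous events out of placebo but left them in the active arms would distort that comparison. This stands, and it is why the change must be confined to the whole-study tables.

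A second objection is that the change exchanges one error for another. In the enumeration, 5,377 of the 10,771 missing-day onsets straddling Week 8 (49.9%) truly began before it. Where the stop date does not help, assigning all of them to drug misplaces about as many as the present rule does. This also stands. The case for changing is direction, not accuracy: in a safety table, doubt should not favour the drug.

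Third, the numbers are likely to be small. Serious events are reported within 24 hours and followed up (protocol 7.3.14), events of special interest follow the same procedure (7.3.15), and adverse events are assessed at both Week 8 and Week 9 (5.12). Serious events and serious infections are therefore the least likely to lack an onset date. Safety data are summarised without statistical comparison unless otherwise specified (SAP 16), and all events are listed. This limits the size of the problem but not its direction.

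Two stronger readings are tempting, and the documents do not support them.

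- A reader might infer that the imputation row serves only Week 8 and almost always returns the treatment phase. It also covers Week 16, and for missing-day dates the split is 54% to 46%.
- A reader might infer that every whole-study safety table is affected. Deaths come from the Death Details page (SAP 16.2) and the QTcF tables from ECG maxima (16.4.1). Neither section refers to the onset algorithm.

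**Conclusion.** The point holds for the whole-study TEAE tables only. In a placebo patient who took extension drug, an event whose partial onset straddles Week 8, or which has no onset date, is always counted under placebo and never under the dose total. The error can only understate events on drug. Dates that straddle only Week 16, and dates whose known parts settle the phase, are not affected.

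The documents give no rate of partial dates, so the total effect cannot be estimated and is probably small. The 4.6 points describe one moved patient under the stated assumptions; they are not a forecast. The percentages in the enumeration rest on uniform dates, but the one-way direction follows from the rule itself. It would be wrong to conclude that the trial's safety comparison is materially biased. Efficacy is untouched. This is a cheap improvement.

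**What to change.** Add one line to SAP Appendix 2, cross-referenced from 16.1.1. For the whole-study tables comparing dose totals with placebo, a TEAE of undeterminable phase in a patient randomised to placebo who took extension drug is counted under that patient's active dose total, unless its stop date precedes the Week 8 visit. Footnote each affected table with the number of events assigned this way. Leave the present rule, identical in all arms, in the randomised treatment-phase tables.

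No new data are needed, since the treatment-emergence table already uses stop dates. Programming is a small branch for the whole-study groups. The cost is that some events that truly began on placebo will be counted on drug, which is the cautious direction for drug safety; the footnote lets a reader judge how much that matters. The line should be added before ambiguous events are reviewed by treatment group.
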